Official Title: The Health Benefits of Indoor Air Filtration Among Children

NCT Number: NCT04835337

Document Date: 2024-09-12

Protocol Synopsis

Title	The Health Benefits of Indoor Air Filtration Among Children
Intervention	Classroom and household air purifiers
Study Objectives	This study aims to explore the health benefits of air purifiers on children's health.
Study Design	The study is a randomized, controlled, double-blind, crossover trial of a multi-setting air purification intervention.
Primary Endpoint(s)	The primary outcomes are cardio-respiratory function including lung function, airway inflammation, blood pressure, heart rate variability, electrocardiograph, academic performances including standardized scores and relative ranking of scores.
Secondary Endpoint(s)	The secondary outcomes are metabolites in exhaled breath condensate, serum protein, cognitive function measured by Wisconsin Card Sorting Test, Attention Network Test, and N-BACK Test, other omics and targeted biomarkers of interest (e.g., CRP, 8-OHdG, etc).
Accrual Objective	105
Study Duration	9 months (from April 2021 to December 2021)
Treatment Description	Participants are divided into an intervention group and a control group according to the principle of cluster randomization. The intervention group is equipped with true-particulate air purifiers and the control group is equipped with sham-purification devices in households and school classrooms.
Inclusion Criteria	(i) Fourth-grade students (10–12 years old) in primary school; (ii) no plans to change schools during the current school year; (iii) those who participate voluntarily and are able to undergo questionnaires and health checks; and (iv) those who have good compliance and accept the installation of an air purifier and PM _{2.5} monitoring equipment at home.
Exclusion Criteria for Individual	(i) transferring schools expected during the study period; (ii) having a chronic disease diagnosed by a doctor within the past year.

Glossary of Abbreviations	5
1. Background and Rationale.....	6
2. Study Objectives.....	6
3. Study Design	6
3.1 Description of Study Design.....	6
3.2 Primary and Secondary Outcomes.....	6
3.3 Stratification, Randomization, and Blinding	6
4. Participants and Sites.....	7
4.1 Inclusion Criteria	7
4.2 Exclusion Criteria for Participant	7
4.3 Sites	7
5. Known and Potential Risks and Benefits to Participants.....	7
6. Intervention	7
6.1 Intervention	7
6.2 Washout Period.....	8

rMSSD	Root mean square of successive differences between adjacent normal cycles
pNN50	Percentage of adjacent NN interval differences greater than 50 ms
VLF	Very low frequency
LF	Low frequency
HF	High frequency
LF/HF	Ratio of LF to HF
PR interval	The interval of the beginning of the P wave to the beginning of the QRS complex
QRS duration	The interval of the beginning of Q wave to the end of the S wave
QT interval	The interval from the onset of the QRS complex to the end of the T wave
QTc interval	The QT correction for rate
RV5	Amplitude of the R wave in lead V5
SV1	S-wave depth in lead V1
RV5+SV1	The sum of the R-wave amplitude in lead V5 and the S-wave amplitude in lead V1

1. Background and Rationale

Previous studies have suggested that fine particulate matter (PM_{2.5}) has adverse effects on children's respiratory, cardiovascular, and cognitive health. However, it is not clear whether reduced PM_{2.5} concentration by indoor air purifiers is beneficial for the multi-system health of school-age children.

2. Study Objectives

This study aims to explore the health benefits of air purifiers on children's health.

3. Study Design

3.1 Description of Study Design

A cluster-randomized, double-blind, crossover trial of a multi-setting (classroom and bedroom) air purification intervention is conducted in Mengzhou City, Henan Province, China, from April 2021 to December 2021. Children aged 10–12 years old (fourth grade) are recruited as subjects. Participants are divided into an intervention group and a control group according to the principle of cluster randomization. The intervention group is equipped with true-particulate air purifiers and the control group is equipped with sham-purification devices both in bedrooms and school classrooms. The two groups receive alternating treatments of true or sham purification in a random order, with each study period separated by a washout period of over two months. A linear mixed-effects model is used to explore the effects of purification intervention. Ambient PM_{2.5} and indoor PM_{2.5} exposure concentrations are monitored in the study.

3.2 Primary and Secondary Outcomes

The primary outcomes for respiratory health are lung function indicators, including forced expiratory volume in 1 s (FEV₁), forced vital capacity (FVC), FEV₁/FVC ratio, peak expiratory flow (PEF), forced expiratory flow at 25–75% of FVC (FEF_{25-75%}), maximal expiratory flow at 75% of FVC (MEF_{75%}), maximal expiratory flow at 50% of FVC (MEF_{50%}), and maximal expiratory flow at 25% of FVC (MEF_{25%}); changes of FeNO; Changes of FeCO. The primary outcomes for cardiovascular health are blood pressure indicators, including systolic blood pressure (SBP), diastolic blood pressure (DBP), mean arterial pressure (MAP) and pulse pressure (PP); heart rate variability indicators, including standard deviation of all normal-to-normal intervals (SDNN), the root mean square of successive differences between adjacent normal cycles (rMSSD), the percentage of adjacent NN interval differences greater than 50 ms (pNN50), very low frequency (VLF), low frequency (LF), high frequency (HF), the ratio of LF to HF (LF/HF); and electrocardiograph parameters, including the interval of the beginning of the P wave to the beginning of the QRS complex (PR interval), the interval of the beginning of Q wave to the end of the S wave (QRS duration), the interval from the onset of the QRS complex to the end of the T wave (QT interval), the QT correction for rate (QTc interval), amplitude of the R wave in lead V5 (RV5), S-wave depth in lead V1 (SV1) and the sum of the R-wave amplitude in lead V5 and the S-wave amplitude in lead V1 (RV5+SV1). The primary outcomes for cognitive health are academic performances, including standardized scores and relative ranking of scores.

The secondary outcomes include the metabolites in exhaled breath condensate, serum protein, the indicators measured by the Wisconsin Card Sorting Test, Attention Network Test, and N-BACK Test. Furthermore, other omics and targeted biomarkers of interest (e.g., CRP, 8-OHdG, etc) are also considered.

3.3 Stratification, Randomization, and Blinding

Students are allocated by class cluster randomization to the intervention group or the control group. The intervention assignment is handed over to independent trained professionals, who do not participate in

any other processes of the trial. Confidentiality of the intervention is maintained for the researcher and participants to achieve double blindness.

4. Participants and Sites

4.1 Inclusion Criteria

Inclusion rules for the study participants are:

1. Fourth-grade students (10–12 years old) in primary school
2. No plans to change schools during the current school year
3. Those who participate voluntarily and are able to undergo questionnaires and health checks
4. Those who have good compliance and accept the installation of air purifiers and PM_{2.5} monitoring equipment at home

4.2 Exclusion Criteria for Participant

The exclusion criteria are as follows:

1. Expecting to transfer schools during the study period
2. Having a chronic disease (including asthma, childhood diabetes, childhood hypertension, behavior-related diseases, etc.) diagnosed by a doctor within the past year.

4.3 Sites

In 2020, the average annual PM_{2.5} concentration of 56 μg/m³ in Jiaozuo City still exceed the annual average PM_{2.5} limit of 35 μg/m³¹. In addition, there are various sources of air pollution in Jiaozuo, including agricultural, industrial and transportation sources. Therefore, Jiaozuo City, Henan Province is selected as the study area.

5. Known and Potential Risks and Benefits to Participants

The medical examination is carried out by professional staff and is demonstrated and explained before the measurements, which does not cause health risks and discomfort. All information and the samples tested about the subject are kept strictly confidential and are only used for this project. Participation in the survey is voluntary, and the rights of respondents who do not agree to participate in this survey, or withdraw at any time after the start of the survey, are not affected in any way.

Respondents receive a feedback report on the results of the medical examination, an air pollution exposure monitoring report, personalized protection advice, and a small gift to thank for participating.

6. Intervention

6.1 Intervention

The intervention group is equipped with purifiers with true-purification (i.e., with high-efficiency particulate air (HEPA) filter), and the control group with sham-purification purifiers (without HEPA filter), which are installed in the classrooms and households of both groups. In the school environment, an air purification efficiency of 850 m³/h (LEXY, KJ901) and a fresh air ventilation with the purification efficiency of 320 m³/h (AIRTAO, AT320) are placed in the front of the classroom and the air purification equipment is the same as the back of classroom. In the home environment, one air purifier with the purification efficiency of 220 m³/h (Haier, KJ210F-A180A) is installed in each of the children's bedroom. Two different treatments are employed, including true-purification and sham-purification, in random order with a washout period of over 2 months. The air purification intervention is performed by trained professionals on and off at regular intervals each day to ensure that the air purification unit is on during the time the children are in the indoor environment. In the event of offline situations such as those caused by poor internet access, the survey respondents are contacted and communicated with promptly. A health examination is conducted at the beginning and end of each study period, and a questionnaire is used to collect basic information about the respondents. We also measured the environmental factors including

PM_{2.5} concentration, temperature, and relative humidity. 24 time-weighted mean PM_{2.5} concentrations are calculated as personal daily exposures for further analysis.

6.2 Washout Period

A total of four surveys are conducted during the study, and the two sets of purifiers are swapped before the third survey to achieve the purpose of elution.

6.3 Biological sample collection and testing

The trained medical staff collect exhaled breath condensate (EBC) before and at the end of each intervention period. EBC samples are stored in a -80°C refrigerator before metabolomics analysis. After the cardiovascular indicator measurements, medical staff collect 6 ml peripheral venous blood. Children are instructed to fast before the blood collection. The blood samples are heated in a water bath and centrifuged, after which the upper serum is extracted in EP tubes and stored in the -80°C freezer before proteomics testing and analysis. Urine, saliva, oral cells, oral swabs, nasal swabs, skin swabs, nails and feces samples are collected during each visit and stored in the -80°C refrigerator before laboratory testing.

6.4 Criteria for discontinuing or modifying

1. The intervention is ended if it is disruptive to the classroom.
2. The participation is voluntary and participants can be withdrawn at any time. Their rights are not affected in any way.

6.5 Strategies for adherence

During the investigation, all tests are conducted by professionally trained medical personnel and all computer-based tests are conducted for children of that age and do not cause any adverse effects.

The physical examination report and environmental test report are returned timely so that the survey subjects can better understand their own health status and environmental exposure, deepen their understanding of the test and better cooperate.

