7.10 Academic achievement measurements

Academic achievement is collected at the beginning and end of each study period. The evaluation of academic performance consisted of standardized scores (maths, chinese and total) and the relative ranking of the scores within the grade. Standardized grades are converted from raw grades by z-scores according to the number of exams and class in order to eliminate differences due to different exams; rankings are converted from place rankings of raw grades, reflecting the relative value of grades.

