8.2 Analytical models

We use a linear mixed-effects model to estimate the effects of air purification intervention or per interquartile range (IQR) decrease in personal PM_{2.5} exposure on several functional indicators and targeted biomarkers of children's health. To account for the impact of varied outcome levels at baseline, the absolute or relative change in outcome level is calculated as the difference between post-intervention and pre-intervention, comparing the change in health outcomes between the intervention and control groups after the intervention. We further adjusted for the confounders including sex, age, body mass index (BMI, kg/m²), temperature (°C), relative humidity (%), etc. A random intercept for each participant is included in the models to account for the repeated measurements.

In addition, we plan to perform metabolomics analysis of EBC samples using ultra-high performance liquid chromatography-tandem mass spectrometry and proteomic analysis of serum samples with 4D-label free technology. Besides, other omics analyses and targeted biomarkers of interest are planned to further explore the potential biological mechanisms.

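### Section 6.5 returns environmental reports to families without fixing timing or content; indoor or personal PM2.5 shown before the fourth survey would be an imperfect but uncontrolled cue to true versus sham purification

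*Combined protocol and SAP*

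**What the plan says.** Section 6.5, under adherence strategies, reads: "The physical examination report and environmental test report are returned timely so that the survey subjects can better understand their own health status". The aim is that subjects grasp "their own health status and environmental exposure, deepen their understanding of the test and better cooperate". Section 5 promises respondents, besides their examination results, "an air pollution exposure monitoring report, personalized protection advice, and a small gift to thank for participating". It gives no date for any of these.

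The arms differ in one physical respect. Section 6.1 gives the intervention group "purifiers with true-purification (i.e., with high-efficiency particulate air (HEPA) filter), and the control group with sham-purification purifiers (without HEPA filter"). Section 7.3 has PM2.5 recorded in bedrooms and classrooms throughout the study and combined with activity diaries into a personal daily exposure.

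On timing of outcomes, section 6.1 says "A health examination is conducted at the beginning and end of each study period", and section 6.2 says "A total of four surveys are conducted during the study, and the two sets of purifiers are swapped before the third survey". Surveys 1 and 2 therefore frame the first period, and surveys 3 and 4 the second.

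The synopsis and section 3.1 call the trial double-blind. Sections 3.3 and 7.2 say that allocation is confidential from researchers and participants. Neither section mentions exposure data sent back to families.

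**The concern.** PM2.5 is the quantity that the filter is meant to change. A family that sees its own bedroom, classroom or personal PM2.5 while outcomes are still being collected has some information about which device it has. Two design features spread that information. Allocation is by class, with the same treatment at school and at home, so one readable report can inform a whole class. And each group receives both treatments, so a correct guess for one period settles the other.

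What is at stake is the double-blind claim, and with it the outcomes that respond to effort or behaviour. Advice tailored to a child's readings, if that is what section 5 means, could also differ by arm and change behaviour such as window opening, which section 6.6 itself links to how well the purifiers work.

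**Working it through.** The plan gives no figure on this point to reproduce. The check sets the sections side by side and then works out where an expectation effect would enter the planned analysis.

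**1. When is the report returned?** Section 6.5 says only that return is timely. Its stated purpose is better cooperation, and a report sent after the last survey could not serve that purpose, so return during the trial is the natural reading. It remains an inference: no section ties the report to a survey.

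**2. What does it contain?** Not stated. Section 6.5 speaks of subjects' own exposure, which suggests indoor or personal values, but an outdoor-only report is not excluded.

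**3. Would such values reveal the arm?** In part. The HEPA filter moves indoor PM2.5, but so do outdoor levels and window opening, and a comparison between periods mixes in season (April to December 2021). Comparing indoor with outdoor readings, or one class with another, would be more telling than a single value.

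**4. Does anything limit it?** Sections 3.3 and 7.2 state confidentiality in general terms. They neither delay the report nor restrict its content.

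**5. Where would bias enter?** Section 8.2 analyses change: "the absolute or relative change in outcome level is calculated as the difference between post-intervention and pre-intervention". Let e1 to e4 be the true-minus-sham difference at surveys 1 to 4 that is due to belief alone, and d its full size at one survey. The documents do not give d. With equally weighted periods:

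- Period 1 shift: C1 = e2 − e1
- Period 2 shift: C2 = e4 − e3
- Shift in the two-period estimate: B = (C1 + C2)/2

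Possible patterns (e1, e2, e3, e4), where x is any constant:

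- Report between surveys 1 and 2, effect equal at surveys 3 and 4: (0, d, x, x), so B = (d + 0)/2 = d/2
- Report between surveys 1 and 2, second period inferred by elimination, effect absent at survey 3 and full at survey 4: (0, d, 0, d), so B = (d + d)/2 = d
- Report between surveys 2 and 3, effect already full at survey 3: (0, 0, d, d), so B = (0 + 0)/2 = 0
- Report between surveys 2 and 3, effect building only with use: (0, 0, 0, d), so B = (0 + d)/2 = d/2
- Report between surveys 3 and 4: (0, 0, 0, d), so B = d/2
- Report after survey 4: (0, 0, 0, 0), so B = 0

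If every e lies between 0 and d and the effect does not fade between the two surveys of a period, C1 and C2 each lie between 0 and d, and so does B, however many reports are sent. Fading would fall outside that range: (0, 0, d, 0) gives B = −d/2. If p is the proportion of families guessing correctly minus the proportion guessing wrongly, d becomes p·d throughout.

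**6. Which outcomes?** Most exposed are coached spirometry with the best effort kept (section 7.6), ranking within the grade (section 7.10) and the computer-based cognitive tests (section 7.11), which are secondary. FeNO, FeCO, blood pressure, heart rate variability and ECG parameters are read from devices and are less exposed to expectation, though a behaviour change that alters exposure could still affect them. Standardized academic scores appear less exposed as well: "Standardized grades are converted from raw grades by z-scores according to the number of exams and class". If that means z-scoring within class, a shift common to a class is removed.

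**The case against.** The strongest reply is that two facts are missing. No section says that the report shows indoor or personal PM2.5, and none says that it is sent before the fourth survey. Section 5 lists the exposure report next to a thank-you gift, which fits feedback at the end of participation, and it may not be the same document as the report in section 6.5. The consent pages, where feedback might be described, are not in the text reviewed. The confidentiality statements could be read as already barring any report that reveals the arm. A family that sees one number has no stated comparator, and many primary outcomes are device-read.

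Most of this stands, and it limits the claim. It does not remove the point. Section 6.5 sets a positive rule to return exposure information promptly, for a purpose that makes sense only during the trial, and a general promise of confidentiality does not tell staff to withhold or edit that report.

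Two stronger readings are tempting. One is that families were unblinded. The documents do not support this: content and timing are unstated, and the cue is noisy. The other is that the bias has a definite size, such as d/2, or a likelihood obtained by counting the intervals between surveys in which a report would do harm. Neither follows. The result depends on an assumed persistence of the effect, the same reporting interval can give different answers, and nothing says which interval is the likely one.

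**Conclusion.** The plan leaves open a route by which participants could infer their arm, and no provision closes it. This is an unaddressed risk to the double blind, not evidence that the blind failed. It is conditional on indoor or personal PM2.5 being shown before the fourth survey.

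Its size cannot be computed from the documents. Under the assumptions in the working (equally weighted periods, belief effect between 0 and d, no fading within a period), the two-period change-score estimate could shift by anything from 0 to d, and by less if only some families infer the arm. Since d is unknown, this shows where bias could enter, not how large it is. The concern bears mainly on spirometry, within-grade ranking and the secondary cognitive tests. The case for acting is that the remedy is cheap and protects a central design claim.

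**What to change.** If the protocol can still be changed, state in sections 6.5 and 5 that reports containing indoor or personal PM2.5, and any advice based on them, go to all participants only after the fourth survey. Examination results can be returned as planned. Any interim environmental report should be limited to the rooftop outdoor readings described in section 7.3, which do not depend on the arm.

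The cost is a short text change in two sections. The downside is that families receive their exposure information, and the study one adherence incentive, later, by at most the 9-month length of the study.

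The planned conduct ended in December 2021 and the document is dated 2024-09-12, so conduct may be complete. In that case, report when environmental reports were sent and what they showed, and qualify the double-blind description if indoor or personal PM2.5 was disclosed before the fourth survey. That costs a few sentences.

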6.6 Permitted or prohibited interventions

During the intervention study period, it is recommended to have less window opening ventilation to ensure the effectiveness of the air purification intervention. If the subject takes medication regularly, it can be carried out normally according to the doctor's instructions.

7. Study Procedures

7.1 Enrollment

The research subjects are surveyed through the screening questionnaire, combined with the above inclusion and exclusion criteria, and the research subjects with good compliance and willingness to complete the study according to the requirements of the project are selected.

7.2 Randomization

Students are allocated by class cluster randomization to the intervention group or the control group. The intervention assignment is handed over to independent trained professional, who does not participate in any other processes of the trial. Confidentiality of the intervention is maintained for the researcher and the survey participants to achieve double blindness.

